To estimate the treatment effect for *longitudinally measured continuous outcomes*, the outcome will usually be defined as “change from baseline” (difference at follow-up visit minus baseline value). The treatment effect through follow-up will then be estimated with 95% confidence intervals using generalized estimating equations (GEE) with an indicator for treatment group, or, in the case of Gaussian responses, the corresponding mixed effects models with random effects for participants. To improve the model fit and reduce error variance, “visit number” (day) may be included as categorical variable in the model; alternatively, “time” may be included as continuous variable. Models will also be adjusted for the baseline values of the outcome variable.

Time-to-event outcomes will be summarized with Kaplan-Meier estimates for cumulative probabilities over time, and compared between treatment groups using stratified log-rank tests or Cox proportional hazards models, or their competing risk analogues.

In case “death” is a competing risk for the outcome (e.g., for time to hospital discharge), the following competing risk methods will be used:

- Aalen-Johannsen estimator for the cumulative incidence function (analogue to the Kaplan-Meier estimate)³
- Gray’s test with $\rho=0$ (analogue to the log-rank test)⁴
- Fine-Gray estimates and tests for the sub-distribution hazard ratio (analogue to the Cox proportional hazards model).^{5,6}

The proportional hazards assumption will be tested by adding an interaction term for time by treatment group to the model. The cumulative proportions of participants who experienced the event will also be compared at given time points (specified in secondary objectives, e.g., at 28 days); in this case, the cumulative proportions will be estimated using Kaplan-Meier estimates or the competing risks analogue, and/or as proportion of participants who reached the time point (e.g., time since randomization ≥ 28 days).

The **administrative follow-up time** is defined as the minimum of (cut date minus randomization date) or the analysis time period. For example, the analysis time period for the time to hospital discharge is 180 days, and the analysis time period for the important safety endpoint, the composite of *grade 3 and 4 events, SAEs, PSESEs, or death*, is 5 days or 28 days. The **administrative censoring date** is the earlier of the cut-date of the dataset or the randomization date plus analysis time period.

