The primary safety outcome of *grade 3 or 4 AEs, SAEs, PSESEs, or death through Day 5* includes potentially infusion-related outcomes; the analysis of the primary safety outcome is described in section 7. The current section describes safety analyses that are focused on the peri-infusion time period (i.e., during and within 2 hours after the infusion).

Peri-infusion signs and symptoms are reported as AEs (with grade and action taken) on eCRFs. Local labs are reported at baseline, Days 1 and 2 for all participants, and Days 3 and 5 if clinically available. Labs on Day 5 are reported for participants who are treated in the ICU.

Side effects of aviptadil observed in previous studies include:

- Hypotension with and without vasopressor
- Diarrhea
- Facial flushing
- Bradycardia
- Tachycardia

For the aviptadil versus placebo comparisons, incidence and management of hypotension in particular will be monitored in detail. Blood pressure is recorded prior to the start of the infusion and every 2 hours peri-infusion on each infusion day. Vasopressor use and dose are reported: prior to the start of the infusion, the highest dose peri-infusion, and the dose at 2 hours after the infusion.

The following data summaries will be provided overall for Days 0-2, and separately by day. Treatment groups will be compared using statistical methods described under “analysis principles” in section 3; comparisons will be stratified by disease severity at study entry (2 categories, by use of *invasive mechanical ventilation or ECMO*).

- Number and percentage of participants with infusion-related signs or symptoms (reported during the infusion or within 2 hours after the infusion), by type and grade, by type and grade cut-off (i.e., \geq grade 2, \geq grade 3, etc.), and by type and action taken.

Comments:

1. For aviptadil, **diarrhea is not included in the composite safety outcome** of incident grade 3 or 4 AEs, SAEs, PSESEs or death unless it is a SAE or leads to discontinuation of the infusion (for the day, or permanent discontinuation). Therefore, peri-infusion diarrhea AEs will be summarized in two ways: (1) as reported, and (2) restricted to diarrhea AEs that lead to discontinuation of the investigational agent.
2. Hypotension, diarrhea, facial flushing, bradycardia, and tachycardia are collected as part of the infusion-related signs and symptoms, and will be summarized by type and grade, and by type and action taken in response to the AE, as described above.

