- **Peri-infusion hypotension summary**

- Peri-infusion hypotension AEs reported on infusion eCRF (by grade: highest grade on Days 0-2, or highest grade on the day for the day-specific summaries)
- Blood pressure (across days 0-2, and on each day)

- MAP decrease by > 20 mmHg from daily pre-infusion baseline
- Lowest peri-infusion MAP (mean [SD] across participants)
- Incidence of MAP < 65 mmHg (compared to daily pre-infusion baseline)
- Percentage of peri-infusion BP data points with MAP <65 mmHg (mean [SD] of percentage across participants)
- Infusion modifications for hypotension (prevalence on ≥ 1 day)
 - Infusion not attempted for hypotension/vasopressor use
 - For those with any infusion modification, summary of the highest-intensity infusion modification (across Days 0-2, and for each day): Rate decreased but infusion not paused; infusion paused but resumed; infusion discontinued for the day; infusion discontinued permanently
- Vasopressor use peri-infusion
 - New peri-infusion vasopressor use on any day among patients not receiving vasopressors pre-infusion on Day 0 (Number in subgroup, N, %)
 - New or increased peri-infusion vasopressor use on any day among patients who received vasopressors pre-infusion on Day 0 (Number in subgroup, N, %)
 - Maximum peri-infusion vasopressor rate increase within a study day from pre-infusion to peak (in NE units; max over Days 0-2, then mean across patients; 0 NE is imputed for time points when no vasopressor is used. If the maximal peri-infusion vasopressor dose is lower than the pre-infusion dose, then 0 NE will be imputed).
 - Percent with vasopressor rate higher at 2 hours post infusion than pre-infusion
 - Incidence of vasopressor rate increase by > 0.03 mcg/kg/min NE units peri-infusion relative to daily pre-infusion baseline (N, %)
 - Incidence of peak (absolute) vasopressor rate of > 0.1 mcg/kg/min NE units
- IV fluid use peri-infusion in response to hypotension AE
 - IV fluid (crystalloid ≥ 500 mL or equivalent colloid volume) peri-infusion, prevalence
 - For those who received IV fluid or colloid: maximum IV fluid volume on one day (max across days for each participant, then mean across participants)
- Summary of *SBP and MAP trajectories*, from infusion start to 2 hours after infusion
 - Mean trajectories will be plotted by treatment group, and compared using longitudinal models.

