 - For selected participants, *individual trajectories* for MAP and SBP will be plotted for each of the infusion days. In particular, individual trajectories will be plotted for participants who used vasopressors, who experienced peri-infusion hypotension (MAP < 65 mmHg or hypotension AE), or for whom the infusion flow rate was decreased, the infusion paused, or discontinued. These events will be marked on the individual trajectories. Thus, the individual trajectories serve as “line listings” for hypotension events.

- Heart rate:
 - Mean trajectories over time, similar to MAP
 - Percent of participants for whom the peri-infusion heart rate decreased to below 60 bpm at any time, stayed between 60-100 bpm at all times, or reached >100 bpm at any time.
- Medications (other than vasopressors) received in response to AEs during or within 2 hours after infusion, number and percentage of participants and type of medication
- Listings of participants who died or experienced grade 3 or 4 AEs, SAEs, or PSESEs are provided as part of the safety analyses described in section 7.

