7.2 Additional Safety Analyses for the Aviptadil Cohort

Limited safety data are available for aviptadil. Therefore, infusion reactions to aviptadil will be carefully monitored. Side effects of aviptadil observed in previous studies include:

- Hypotension with and without vasopressor
- Diarrhea
- Facial flushing
- Bradycardia
- Tachycardia

Data summaries that address these potential side effects during or within 2 hours after the infusion are described in section 6.1, under “Safety”.

In addition, the aviptadil and placebo groups will be compared for *hypotension associated with organ dysfunction* within the first 5 days after study entry. *Hypotension associated with organ dysfunction* is defined as hypotension plus concomitant or subsequent organ dysfunction. Organ dysfunction in this setting is a composite outcome consisting of items 5a-5f (excluding item 5b4) of the secondary outcome of *clinical organ failure and serious infections* (section 4.1.2 of the TESICO master protocol). The composite outcome will be assessed on Day 5, and compared between treatment groups using CMH tests, stratified by

disease severity at baseline; the ORs will be estimated with 95% CIs using logistic regression, adjusted for disease severity at baseline.

8 Efficacy Analyses

Analysis cohorts: Separate efficacy analyses will be conducted for the **Aviptadil** cohort (comparison of aviptadil versus placebo), and the **Remdesivir** cohort (comparison of remdesivir versus placebo). Interactions between aviptadil and remdesivir will be assessed in the **Factorial** cohort (assessment whether the effects of aviptadil and remdesivir are independent of each other, section 9).

Efficacy analyses will be by intention-to-treat, unless otherwise stated.

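### The categorical peri-infusion heart-rate summary for aviptadil takes no account of the pre-infusion rate, which makes this one descriptive safety summary less sensitive than it could be.

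*SAP*

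**What the plan says.** SAP section 7.2 introduces a list with "Side effects of aviptadil observed in previous studies include"; bradycardia and tachycardia are both on it. The data summaries for these effects are in section 6.1, under the safety heading.

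For heart rate, section 6.1 plans two items:

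- "Mean trajectories over time, similar to MAP". For blood pressure the same section says: "Mean trajectories will be plotted by treatment group, and compared using longitudinal models". Section 3 (Analysis Principles) adds, for longitudinal continuous outcomes: "Models will also be adjusted for the baseline values of the outcome variable".
- A categorical count: "Percent of participants for whom the peri-infusion heart rate decreased to below 60 bpm at any time", staying within 60 to 100 throughout, "or reached >100 bpm at any time". No pre-infusion value and no at-risk subset is named.

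Several hypotension items in section 6.1 do use a pre-infusion reference. One is "MAP decrease by > 20 mmHg from daily pre-infusion baseline". The incidence of MAP below 65 mmHg is also set against the daily pre-infusion value, and new vasopressor use is counted only among participants not on vasopressors before the Day 0 infusion.

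Section 6.1 also says: "Hypotension, diarrhea, facial flushing, bradycardia, and tachycardia are collected as part of the infusion-related signs and symptoms". These are summarised by type and grade and by action taken. Footnote a of Table D-1 (Appendix D) records adverse events of any grade present on Day 0 before the first infusion, so that new ones can be recognised.

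**The concern.** The verbs in the categorical item suggest a change, but the rule tests only a level. A participant at 115 bpm before the infusion who stays there is counted as having reached more than 100. In patients with critical respiratory failure some will start above 100, and they are near-certain events in both arms. They add noise and no contrast, so a real effect of aviptadil on heart rate looks smaller in this table than it is among those who could newly cross the threshold. Two programmers could also implement the item differently, one reading it as a level and the other as a crossing.

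The outer groups can overlap as well, since one participant can fall below 60 and later exceed 100. The percentages therefore need not add to 100, although the item reads like a three-way split.

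What is at stake is the sensitivity of one table that the DSMB uses to watch for a listed side effect. Type I error and the primary analysis are not affected.

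**Working it through.** The SAP gives no rate, effect size or power for this item, so there is no planned figure to reproduce. The calculation below is an illustration.

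**Inputs from the SAP.** The cut-off is 100 bpm (section 6.1). The group size is 320 (section 1.4). Tests are two-sided at 0.05, and binary outcomes are compared by CMH test or logistic regression (section 3).

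**Assumptions, none of them in the SAP.** A share *b* of each arm is above 100 bpm before the first infusion, and 95% of these exceed 100 again in either arm. Among the rest, 15% (placebo) and 25% (aviptadil) newly exceed 100.

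**Rule as written.** Placebo proportion = 0.95*b* + 0.15(1 − *b*). Aviptadil proportion = 0.95*b* + 0.25(1 − *b*). The 0.95*b* term cancels in the difference, which is 0.10(1 − *b*). The contrast shrinks by exactly the share already above 100.

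**New-onset rule.** 15% against 25% among 320(1 − *b*) per arm.

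**Power.** Normal approximation with unpooled variance: Φ(difference/SE − 1.96).

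At *b* = 0.30:

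- As written: placebo 0.285 + 0.105 = 39.0%; aviptadil 0.285 + 0.175 = 46.0%. SE = √[(0.39×0.61 + 0.46×0.54)/320] = 0.0390. Power = Φ(0.07/0.0390 − 1.96) = 43%. Odds ratio 1.33.
- New onset: 320 × 0.70 = 224 per arm. SE = √[(0.15×0.85 + 0.25×0.75)/224] = 0.0375. Power = Φ(0.10/0.0375 − 1.96) = 76%. Odds ratio 1.89.

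| Share above 100 before infusion | As written: placebo vs aviptadil | Difference (points) | Power as written | New-onset n per arm | Power, new onset |
|---|---|---|---|---|---|
| 15% | 27.0% vs 35.5% | 8.5 | 64% | 272 | 84% |
| 30% | 39.0% vs 46.0% | 7.0 | 43% | 224 | 76% |
| 45% | 51.0% vs 56.5% | 5.5 | 29% | 176 | 66% |

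**Other assumptions.** With new-onset rates of 20% and 30%, everyone already above 100 still counted, and a pooled variance under the null, power as written against new onset is 68% against 79% at *b* = 10%, 43% against 69% at 30%, and 26% against 54% at 50%. With a larger effect (20% against 40%) and *b* = 30%, it is 95% against 99.7%, so little is lost. With 20 per arm, 20% against 30% and *b* = 30%, it is 6% against 9%. If nobody starts above 100, nothing is lost.

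**Bradycardia.** Assume 5% against 10% new events and 320 per arm, by the same pooled-variance method. If 2% start below 60, the difference is 0.98 × 5 = 4.9 points and power is 57% against 66%. If 5% do, it is 0.95 × 5 = 4.75 points and 45% against 65%. The difference barely moves, but for a rare event even a small prevalent share adds noise. The loss is probably smaller than for tachycardia only if few participants start below 60, and the SAP does not give that share either. If the wording is read as requiring a fall, there is no dilution at this end.

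**The case against.** The strongest reply is that this table is not the only view of the signal. Tachycardia and bradycardia are also graded adverse events, with those present before the first infusion on record. The weekly DSMB report (section 2) names peri-infusion grade 1 to 4 adverse events and does not name this table. Mean heart-rate trajectories are compared with models that section 3 adjusts for baseline. If normality is assumed, 15% against 25% corresponds to a shift of about 0.36 SD (1.04 − 0.67). A continuous comparison of 320 per arm would detect that with about 99% power, or about 63% if the average shift were half as large. Section 6.1 also mixes relative and absolute items for blood pressure and vasopressors, and says that hypotension in particular gets detailed monitoring.

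Most of this stands. A reader might infer that tachycardia and bradycardia are assessed only from absolute heart rate, or that the DSMB would miss an effect. The documents support neither reading.

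It does not make the item redundant. Rises in some participants and falls in others can cancel in a mean, and both are listed side effects. Adverse-event counts depend on someone recording the event. The peri-infusion summary in section 6.1 does not say that it is limited to new events; the explicit baseline exclusion in section 7.1 is for incident grade 3 and 4 events. The categorical item is the only planned summary of measured heart rate that separates the two directions.

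Two further objections are fair. New-onset rows leave out participants already above 100, so a rise from 115 to 145 would not show there. And section 6.1 states pre-infusion recording on each infusion day for blood pressure, but not for heart rate.

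**Conclusion.** The point holds as a minor improvement to a descriptive DSMB summary. As written, the categorical item has no pre-infusion reference, and its risk difference for high heart rate shrinks by the share already above 100 bpm. Under the stated assumptions that costs about 20 to 37 percentage points of power in this one comparison (84 − 64 at a 15% share; 66 − 29 at 45%).

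The direction follows from arithmetic if any participants start above 100, those participants exceed it about equally often in both arms, and the drug effect lies among the rest. The size rests wholly on assumed rates. At the first review of about 40 participants neither rule would have useful power.

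A reader might also infer that the comparison is biased. It is not: under randomisation the prevalent cases fall equally on both arms in expectation, and under the null neither arm is favoured.

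**What to change.** Add two rows to the heart-rate summary in SAP section 6.1:

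- new peri-infusion heart rate above 100 bpm, among participants at or below 100 bpm on the Day 0 pre-infusion (or baseline) reading;
- new peri-infusion heart rate below 60 bpm, among participants at or above 60 bpm on that reading.

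This follows the SAP's own construction for new vasopressor use. A Day 0 reference is taken before any study drug, so the subset is defined independently of treatment; a Day 1 or Day 2 reference could already reflect the previous day's infusion.

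Name the reading used and confirm that it is available. Section 5 lists heart rate among the baseline vital signs, and Appendix E schedules vital signs on Day 0. Section 5 splits baseline heart rate at below 100 against 100 or more, so the subset should be formed from the recorded value and not from that category.

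Keep the absolute percentages for all participants, labelled as separate, non-exclusive items, so that those already beyond a threshold are still shown.

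The cost is SAP wording and table programming, with no new visits if the reading is confirmed. The drawback is a smaller denominator for the new-onset rows.

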6.2 Infusion of Remdesivir (Active or Placebo)

Study population (Remdesivir cohort, mITT): Unless otherwise noted, the study population consists of participants who were randomized to remdesivir or its placebo, excluding those who did not receive **any** remdesivir/placebo (modified intention-to-treat [mITT]).

Remdesivir (and its placebo) will be administered once-daily by intravenous infusion (over 30 minutes) for up to 10 days, or until hospital discharge, whichever comes sooner. Remdesivir will be administered on Day 0 as a 200 mg IV loading dose, followed by a 100 mg maintenance dose on subsequent days. Remdesivir may be discontinued after 5 or more days, per discretion of the treating clinician, if the participant is no longer requiring respiratory support.

In this section, “remdesivir” refers to the blinded remdesivir infusion (active or placebo).

The following statistics will be used to summarize the infusions in each treatment group (active and placebo) for the closed reports, or pooled across treatment groups for reports shared with investigators:

- Number and percent of participants who received (any) remdesivir/placebo, by day
- Number of days remdesivir was administered: median, IQR, distribution.
- Number and percent of participants for whom remdesivir was discontinued, and reasons for discontinuation.
- Number and percent of participants for whom the complete target volume was not administered, by day; and reasons for incomplete administration (pooled over days).
- Number and percent of participants for whom a daily remdesivir infusion was discontinued prematurely, by day, and pooled across days.
- Pooled across days:
 - Number and percentage of participants with infusion-related signs or symptoms (reported during the infusion or within 2 hours after the infusion), by type and grade, and by type and action taken. (Closed report only)
 - Number and percent of participants for whom a remdesivir infusion was discontinued prematurely due to an AE

- Number and percent of participants for whom medications were prescribed during or within 2 hours following the infusion *in response to an AE*, and type of medication

7 Safety Analyses

The planned timing of safety reviews is described in section 2. An overview of the safety data collection is provided in [Appendix D](#).

Analysis cohorts: Safety analyses will be conducted by modified intention-to-treat (mITT), unless otherwise stated, for the following three cohorts:

1. **Aviptadil cohort, mITT:** Participants who were randomized to aviptadil or its placebo, excluding those who did not receive any aviptadil/placebo
2. **Remdesivir cohort, mITT:** Participants who were randomized to remdesivir or its placebo, excluding those who did not receive any remdesivir/placebo
3. **Factorial cohort, mITT:** Participants who were randomized to the four treatment combinations formed by the aviptadil/placebo and remdesivir/placebo pairs (2x2 factorial design), excluding those who did not receive any of the aviptadil/placebo OR any of the remdesivir/placebo.

In the factorial cohort, the presence of interactions between aviptadil and remdesivir will be assessed, for the primary safety endpoint and other key outcomes. If there is evidence for interactions ($p<0.05$) in a given outcome, the analyses described in Section 9 will be performed.

Comment: Because the safety profile of remdesivir has been well-described, safety summaries for the remdesivir cohort will be provided only after more than 40 participants are randomized to remdesivir vs placebo; the frequency of the safety reports for remdesivir will be determined by the DSMB.

A comprehensive safety review includes:

- Comparison of the treatment groups for the primary safety endpoint, its components, and analyses of secondary safety outcomes (described in this section)
- Analyses of infusion-related reactions and symptoms, described in section 6
- Evaluation of selected efficacy outcomes (e.g., recovery at Day 90, time to recovery, time to hospital discharge), which contain important safety information. Described in section 8.

In addition to the full DSMB reviews, more frequent, shorter safety reports will be provided to the DSMB, for example, weekly safety reports early in the trial.

This section describes the primary safety outcome, and the analyses of AEs, SAEs, UPs, SUSARs, and deaths. Comparisons between treatment groups will be stratified by disease severity at study entry (as described in section 3 under “stratification”).

In order to streamline the reporting of events, it was decided that certain protocol-specified exempt events (PSESE) are *not reported as SAEs*, unless they are considered related to the study treatment by the investigator. The PSESE in TESICO encompass a collection of serious events that are expected to occur commonly in the target population even in the absence of study interventions. While the PSESEs in this protocol are similar in severity to

SAEs, PSESEs are reported not on the SAE eCRF, but are reported as study endpoints on various other eCRFs. AEs that are considered PSESEs are listed in [Appendix C](#). The composite outcome of *clinical organ failure or serious infections*, defined in [Appendix B](#), is comprised of all PSESEs, except all-cause mortality (death is a PSESE, but is included in the composite of *clinical organ failure or serious infections* only if the cause of death corresponds to one of the components listed in [Appendix B](#)).

